6.0 Study Procedures

6.1 Informed Consent

Subjects will need to sign an informed consent form that has been approved by both the Sponsor and reviewing IRB to be considered for participation in this study. Subjects must meet all of the inclusion and none of the exclusion criteria.

Each subject (or a legally authorized representative) must give written consent, in accordance with local requirements, after the nature of the study has been fully explained and questions answered. The consent form must be signed prior to any study-related procedures, and the process of informed consent must be documented in the medical record.

6.2 Demographics & Medical History

Demographics will be collected including age, ethnicity, race, and sex. Significant medical history, including lipedema and lymphedema history, will be collected.

6.3 Laboratory Testing

Any women who are not surgically sterile or ≥ 1 year post-menopause will be tested for pregnancy according to the site specific procedures at the Baseline visit. If the pregnancy test is positive, the subject will not be enrolled in the study.

Subjects must agree to use one of the following forms of birth control prior to starting and during treatment with the Flexitouch:

- Abstinence (not having sexual relations with a person of the opposite sex)
- Implantable hormone (e.g. Norplant)
- Intrauterine Device
- Male partner must have a vasectomy
- Female sterilization
- Hormonal injection
- Oral contraceptives

6.4 Vital Signs

Height and weight (without shoes or coat) will be collected at Baseline and Follow-up. Results will be recorded on the respective data collection forms. If the BMI is > 50 at the Baseline visit, the subject will not be enrolled in the study.

6.5 Randomization

If the subject meets all of the inclusion criteria and none of the exclusion criteria, they will be randomly assigned to Flexitouch Plus with conservative care or conservative care alone. Randomization codes will be generated in a permuted block design. The block size will be balanced within each block, and will maintain a 1:1 ratio between the treatment groups.

The randomization code will be distributed by sealed envelope and assigned sequentially as soon as an eligible subject completes the Baseline measurements. The appropriate staff member will obtain the next sequentially sealed randomization envelope and open it while the subject is present.

The randomization assignment cannot be changed or chosen by the subject or the investigator. The randomization envelope, as well as evidence of treatment group assignment, should be placed in the subject's binder.

6.6 InBody 770 Bioimpedance Measurements

The InBody is a medical-grade bioimpedance device that measures body water and composition, providing objective measures of fluid and muscle-fat balance. The unit is non-invasive and generates a comprehensive results sheet that provides accurate, objective, and easily understandable measurements in less than 60 seconds to evaluate a patient's current health status and track efficacy of treatments and interventions. Clinicians can use the InBody to: monitor body water and composition for early detection and treatment of lymphedema, identify fluid imbalances through tracking segmental body water values and edema index variables, and evaluate additional health risks related to muscle-fat balance.

For the purposes of this study, bioimpedance measurements will be collected at the beginning of the Baseline and Follow-up visit (immediately before and after removal of graduated compression). Subjects will be asked to:

- Stand on the InBody 770 with graduation compression on (covering the foot and heel pads while holding the hand pieces). The arms will then be raised up and away from the trunk for 20 seconds while the testing begins.
- Remove shoes and socks, clean hands and feet with a wipe, and stand on the InBody 770 (covering the foot and heel pads while holding the hand pieces). The arms will then be raised up and away from the trunk for 20 seconds while the testing begins.

Data from the Body Water and Composition Analysis will be recorded on the respective data collection forms and a copy of each comprehensive results sheet will be retained in the subject's medical record (Figure 2 and 3).

InBody 770 Results Interpretation | 60-Second Body Water Analysis

[figure not shown]

Figure 2. Body Water Analysis

InBody 770 Results Interpretation | 60-Second Body Composition Analysis

[figure not shown]

Figure 3. Body Composition Analysis

At the Follow-up visit, additional bioimpedance measurements (including whole body ECW/TBW ratio, as well as segmental ratios for the Right/Left Arm, Right/Left Leg, and Trunk) may be collected immediately after an approximately 60-minute in-clinic treatment with FT Plus. The measurements will be collected and recorded in the same fashion outlined above.

Generally speaking, if there is any type of inflammation or water retention occurring in the body, body water will accumulate in the extracellular space. Thus, injuries, disease, aging, high sodium diets, as well as low muscle mass, will cause the ECW/TBW to increase. The unit renders a whole body ECW/TBW ratio, as well as segmental ratios for the Right/Left Arm, Right/Left Leg, and Trunk. A whole body or segmental ECW/TBW ratio of >0.39 is considered abnormal. The segmental ratios are used to identify problem areas for fluid retention and inflammation. A 0.005 difference in ECW/TBW between right and left limbs may be indicative of inflammation or water retention. Larger discrepancies are required between upper and lower body given the legs have a slightly higher ECW/TBW ratio due to gravity and increased blood volume.

6.7 Circumferential Measurements

Circumferential measurements will be taken at Baseline and Follow-up per standard care at the beginning of the visit at 4 sites on each leg (immediately after bioimpedance measurements and the removal of graduated compression), 1 site at the hips, and 1 site at the waist (for a total of 10 measurements) using a Gulick II tape measure. Sites include:

- Site 1=narrowest part of the ankle (right and left leg),
- Site 2=largest part of the calf (right and left leg),
- Site 3=top of knee cap for lower thigh (right and left leg),
- Site 4=thickest part of the upper thigh (right and left leg),
- Site 5=widest part of the hips, and
- Site 6=narrowest part of the waist.

Results will be recorded in centimeters on the respective data collection form.

At the Follow-up visit, additional circumferential measurements (including 4 sites on each leg, 1 site at the hips, and 1 site at the waist using a Gulick II tape measure) may be collected immediately after an approximately 60-minute in-clinic treatment with FT Plus. The measurements will be collected and recorded in the same fashion outlined above. .

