6.9 QOL, Symptoms, Mobility & Pain Assessments

The following assessments will be completed by the subject at the Baseline and Follow-up visits. Subjects will be instructed to answer all of the items (i.e., questions or statements) presented. Prior to departure, study personnel will review each assessment for missing data to ensure the subject addressed each item.

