6.10 Treatment

Following randomization, collection of measurements, and the completion of questionnaires, patients will be trained on the conservative care prescribed by the investigator (or designee).

Patients randomized to the Flexitouch Plus will obtain a device through standard commercial means (via self-pay, patient assistance, or insurance programs). The standard prescription of ‘Full Leg and Core (L1)’ with daily simultaneous bilateral lower extremity treatment (~60 minutes) at normal pressure levels will be used unless alternate programming is selected by the investigator. Alternate programming (e.g., twice daily, high pressure, additional supplemental lower leg program, etc.) may be used at the investigators discretion if a subject reports inadequate control of lymphedema symptoms prior to the next study visit. While alternate programming is not expected to be necessary, it is important subjects have access to the best care possible at all times in a “real world” study.

Once the prescription is submitted/processed at the Baseline visit, device shipment and training on device use must take place within 60 days or the subject will not be enrolled in the study.

At the Follow-up visit, some or all subjects may receive an in-clinic treatment with Flexitouch Plus after the Follow-up data collection is complete. Additional circumferential (including 4 sites on each leg, 1 site at the hips, and 1 site at the waist using a Gulick II tape measure) and bioimpedance (including whole body ECW/TBW ratio, as well as segmental ratios for the Right/Left Arm, Right/Left Leg, and Trunk) measurements may be collected and recorded immediately after completion of the in-clinic Flexitouch Plus treatment.

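### The InBody and tape readings open each visit, the questionnaires have no fixed place, and nothing keeps the readings from the woman before she answers

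*Combined protocol and SAP*

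**What the plan says.** Section 6.6 states that "bioimpedance measurements will be collected at the beginning of the Baseline and Follow-up visit". Section 6.7 states that "Circumferential measurements will be taken at Baseline and Follow-up per standard care at the beginning of the visit", and places the leg readings "immediately after bioimpedance measurements and the removal of graduated compression". Both sets of readings are thus fixed at the opening of Baseline and of Follow-up.

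For the questionnaires, section 6.9 says only that "The following assessments will be completed by the subject at the Baseline and Follow-up visits". Its one further timing remark is an end point: "Prior to departure, study personnel will review each assessment for missing data".

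Section 6.6 describes the InBody as a unit that "generates a comprehensive results sheet that provides accurate, objective, and easily understandable measurements in less than 60 seconds". The sheet is filed in the medical record and the tape values go on a data form. No section says whether the woman may see either.

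Allocation is open. Section 6.5 has the envelope opened in the subject's presence, and section 4.0 describes a comparison with conservative care and no sham. Under section 4.1, two of the three primary endpoint groups are self-reported: quality of life, and symptoms and pain. PROMIS Mobility is exploratory.

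**The concern.** If the readings come first and the forms later, a woman who knows her arm may also know her readings when she rates her swelling, heaviness and pain. At Baseline there is no earlier study reading to compare with. At Follow-up there is, so feedback on change can arise only there, and it would enter the within-group change from Baseline, which section 13.2 makes the primary analysis. If girth change or expectation differs between arms, it would also enter the ANCOVA contrast.

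Section 13.2 relies on point estimates and 95% confidence intervals. A systematic shift moves the estimate without widening the interval, so the report would not reveal it. Agreement between girth and symptoms would also be weaker corroboration if one could have informed the other.

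**Working it through.** **Order within the visit.**
- Sections 6.6 and 6.7: InBody, then tape, at the start of both visits.
- Section 6.9: questionnaires at both visits, place not stated, checked before the woman leaves.
- Table 1: measurements are listed above questionnaires, but the table is not a sequence. It lists tape above bioimpedance, the reverse of 6.7.
- Section 6.10: "Following randomization, collection of measurements, and the completion of questionnaires, patients will be trained on the conservative care". This names measurements before questionnaires, but it concerns Baseline only. It also names randomization first, whereas 6.5 randomizes once the Baseline measurements are complete.

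Readings first is therefore explicit. Forms second at Follow-up is the natural inference, but it is not a rule.

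**Disclosure.** No text says that the day's readings or the Baseline values are shown to the woman, and none says they are withheld. The optional in-clinic session and its repeat readings are not part of the problem, because 6.10 places them after Follow-up data collection.

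**Exposure by instrument.**
- Numerical rating scale (Appendix E): asks about the legs at the moment of answering and includes swelling and heaviness, close to what has just been measured. Most exposed.
- Wong-Baker (Appendix D): asks about present pain. Also exposed.
- RAND-36 (Appendix A): most time-framed items look back 4 weeks. Less exposed.
- PROMIS Pain Interference (Appendix C): looks back 7 days. Less exposed.
- PROMIS Mobility (Appendix B): asks about capacity. Less exposed, and exploratory.

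**The plan's own figure.** Section 13.1 aims for a 95% interval half-width of about 0.40 SD with 15 subjects, counted as 30 legs, per group. With legs treated as independent, half-width/SD = t(0.975, n−1)/√n = 2.045/√30 = 0.373 (or 1.960/√30 = 0.358 with the normal quantile), which is consistent with the plan. For an outcome with one score per woman, n = 15 and the half-width is 2.145/√15 = 0.554 SD. That applies to RAND-36, both PROMIS forms and Wong-Baker.

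**Illustration, with the size assumed.** Suppose there is no true change and feedback shifts the mean change score by b SD.
- Paired t-test on 15 women (14 df, noncentrality b√15): b = 0.1, 0.2, 0.3 gives noncentrality 0.387, 0.775, 1.162, and p < 0.05 in 6.5%, 11.2%, 19.2% of trials instead of 5%.
- Shift in one arm only, two-sample t-test on change (28 df, noncentrality b/√(2/15)): noncentrality 0.274, 0.548, 0.822, and p < 0.05 in 5.8%, 8.3%, 12.5%.

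Nothing in the documents supports one value of b over another, and one shift would not apply equally to all five instruments.

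**The case against.** The strongest reply is that neither the order nor the disclosure is documented. A reader might infer that the woman fills in the Follow-up forms after learning that her legs have shrunk. The documents do not support that. Section 6.9 sets no order, and the phrase in 6.10, "Following randomization, collection of measurements, and the completion of questionnaires", is Baseline text that conflicts with 6.5 over randomization. To know that her legs had shrunk she would need her Baseline values as well as the day's readings. Percent reduction is an analysis calculation in 4.1, and the InBody endpoint is a body-water ratio, not girth. Section 6.6 presents the unit as a tool for clinicians. All of this stands, and it limits the point to what the protocol leaves open.

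It is also fair that open-label self-report with no sham carries expectation bias in any order, and that section 13.2 frames the study as exploratory. Re-ordering removes one avoidable addition to that bias, not the bias itself.

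A practical objection concerns compression. It comes off during the opening InBody step, so putting 36 + 15 + 6 + 1 + 12 = 70 items first could mean that tightness, swelling and heaviness are rated with compression on. Section 2.3.2 leaves compression use uncontrolled. This is a real side effect, but it is met by recording the compression state and holding it constant across visits.

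**Conclusion.** The point holds as a gap in the procedures. The readings are placed first, the forms have no fixed place, and no rule withholds results, so in an open-label trial knowledge of the readings could influence self-reported primary outcomes. The risk is most direct for the numerical rating scale and Wong-Baker. It rests on two assumptions: that sites follow the natural order, and that some women learn their readings.

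The size is unknown. A reader might set an assumed shift against the 0.40 SD half-width and quote the ratio. That would mislead, because 0.40 SD rests on counting legs, most of the self-reported instruments give one score per woman (0.554 SD at n = 15), and the shift itself has no source in the documents. The error rates above show only that a modest shift would matter at this sample size. This is a cheap improvement, not a defect that undermines the trial.

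**What to change.** In 6.9, with matching text in 6.6 and 6.7, state that at both visits:
- Appendices A to E are completed before bioimpedance, tape and exam; at Baseline, this is after consent and before the randomization envelope is opened.
- Current and prior readings are neither shown to nor discussed with the woman until the forms are collected.
- Whether compression is on or off when the momentary items are answered is recorded, and is kept the same at Baseline and Follow-up.

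Reconcile 6.5 and 6.10 on whether randomization precedes the Baseline measurements and questionnaires, since Baseline self-ratings given after the envelope is opened would also be affected.

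The cost is a few sentences and a slightly later start to the physical readings, equally at both visits. No subjects, visits or instruments are added and the sample size is unchanged.

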4.1 Endpoint Mapping

Endpoint	Outcome Measure	Analysis
Primary	
 Circumferential Measurements 	
 Calculate percent reduction at Follow-up compared to Baseline for 6 sites on each leg as well as a composite total.
Primary	
 Quality of Life 	
 Compare Follow-up RAND SF36 score to Baseline.¹
Primary	
 Symptoms & Pain Intensity 	
 Compare Follow-up PROMIS Pain Interference², Wong-Baker Faces Scale, and the NIH Toolbox numerical rating scale (NRS) scores to Baseline.
Exploratory	
 Mobility 	
 Compare Follow-up PROMIS Mobility score to Baseline.²

¹ https://www.rand.org/health-care/surveys_tools/mos/36-item-short-form/scoring.html

² http://www.healthmeasures.net/index.php?option=com_instruments&task=Search.pagination&Itemid=992

Endpoint	Outcome Measure	Analysis
Exploratory	
 • Bioimpedance Measurements 	
 • Calculate mean reduction at Follow-up compared to Baseline for the Segmental (Right/Left Arm/Leg, Trunk) and Whole Body Extracellular Water (ECW)/Total Body Water (TBW) ratios.

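### Eight of the ten girth readings are single tapes at a level found afresh at Follow-up, and neither the Baseline values nor the arm is withheld from the measurer

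*Combined protocol and SAP*

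**What the plan says.** Protocol section 6.7 defines six sites. Five are set by an extreme of girth. On each leg these are the smallest ankle girth, the biggest calf girth and, for the thigh, "Site 4=thickest part of the upper thigh (right and left leg". On the trunk they are the broadest level of the hips and, in the section's own terms, "Site 6=narrowest part of the waist". The one exception is tied to a landmark: "Site 3=top of knee cap for lower thigh (right and left leg".

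Sites 1-4 are taped on both legs and Sites 5 and 6 once each, giving 10 readings per visit with a Gulick II tape. The section describes this as standard care. It gives no repeat reading, recorded level, skin mark or same-assessor rule.

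Section 4.1 makes girth a primary endpoint: "Calculate percent reduction at Follow-up compared to Baseline", by site and as a composite. The other primary endpoints are questionnaires that the subject completes (sections 3.0 and 6.9). Bioimpedance, which a machine reads, is exploratory.

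Under section 6.5 the envelope is assigned once Baseline measurements are complete. A staff member must "open it while the subject is present", and evidence of the assignment goes into the subject's binder. Masking is not mentioned anywhere. Section 13.2 makes paired within-group change the primary analysis and the between-group ANCOVA secondary.

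**The concern.** The endpoint is the difference between two single tapes. If the second is not at the same level as the first, part of the change is tape position. When this is random it adds variance. The measurer also has some freedom in deciding where the extreme lies, and may know both the earlier number and the arm, so expectation can enter the Follow-up reading. A within-group paired analysis cannot separate a systematic Follow-up under-reading from a true reduction, because the control arm plays no part in it.

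The population makes re-location harder. Section 6.8 describes an uneven surface at Stage 2 and overhanging tissue on the thighs and around the knees at Stage 3, and a BMI up to 50 is allowed.

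**Working it through.** **Count of extremum readings.** Sites 1, 2 and 4 on two legs give 3 x 2 = 6; hips and waist add 2. That is 8 of 10 readings and 5 of 6 site definitions. Only Site 3 has a landmark.

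**The plan's own precision figure (section 13.1).** The target is a 95% half-width of about 0.40 SD with 15 subjects, or 30 legs, per group. Half-width = t/√n. For 30 legs this is 2.045/√30 = 0.373 SD, which agrees with the plan if the two legs of a subject are treated as independent. With 15 subjects as units it is 2.145/√15 = 0.554 SD.

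**Random re-location error.** The documents give no SD of change and no tape error, so the error ratio is assumed. Let e be the error SD of one reading divided by the SD of true change. The observed SD of change grows by √(1 + 2e²). If each visit uses the mean of two readings with independent errors, it grows by √(1 + e²). Half-widths for 30 legs, in true-change SDs:

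| e | SD factor, one reading | Half-width | SD factor, mean of two | Half-width |
|---|---|---|---|---|
| 0 | 1.00 | 0.373 | 1.00 | 0.373 |
| 0.25 | 1.06 | 0.396 | 1.03 | 0.385 |
| 0.5 | 1.22 | 0.457 | 1.12 | 0.417 |
| 1.0 | 1.73 | 0.647 | 1.41 | 0.528 |

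The plan states its target relative to the observed SD, which already contains this error. The target would therefore still appear to be met while the interval in centimetres or percent became wider.

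**Systematic Follow-up under-reading with no true change.** Let b be the bias in SDs of observed change. The chance that a two-sided 5% test rejects comes from the non-central t, with non-centrality b√n for the paired test and b√(n/2) for a two-sample test standing in for the ANCOVA:

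| b (assumed) | Paired, 15 subjects | Paired, 30 legs as independent | Between arms, bias in one arm, 15 per arm |
|---|---|---|---|
| 0.1 | 6.5% | 8.3% | 5.8% |
| 0.2 | 11.2% | 18.5% | 8.3% |
| 0.3 | 19.2% | 35.5% | 12.5% |
| 0.4 | 30.3% | 56.3% | 18.5% |
| 0.5 | 43.8% | 75.4% | 26.2% |

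The values of b are a range, not an estimate.

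**Tape level at Site 4.** Assume girth changes by 0.5-1.0 cm per cm of height and the thigh measures 60 cm. A 2 cm difference in level gives 2 x 0.5 to 2 x 1.0 = 1-2 cm, and 1/60 to 2/60 = 1.7-3.3%. This needs a slope at the tape. At an interior maximum or minimum the slope is near zero, so the figure could apply only to Site 4 (2 of 10 readings), and only if girth is still rising where the tape is placed.

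**Direction of an incomplete search at Follow-up.** Missing a maximum reads low at calf, thigh and hips (2 + 2 + 1 = 5 readings), which looks like a reduction. Missing a minimum reads high at ankle and waist (2 + 1 = 3 readings), which hides one. In a composite these partly offset.

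**The case against.** The strongest reply is that an extremum is a well-defined target. Near it girth is flat, so a small misplacement matters little, and errors at ankle and waist run against the device. This stands, and it limits the taper figure to Site 4. Nor is the landmark site beyond doubt, since Stage 3 tissue overhangs around the knee as well.

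A second reply is that the study is unpowered and exploratory, with bioimpedance at the same visits as a cross-check. That lowers the stakes. But section 13.2 makes point estimates and 95% intervals the main product, and an interval does not reveal bias.

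A third is that standard care may include a site method for finding the level. It may, but a method that is not written down cannot be checked or repeated.

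A reader might also infer that staff judge the level by eye, or that the people who train the subject also tape her. The documents say neither: section 6.7 does not state how the extreme is found, and section 6.10 does not say who gives device training. A reader might further infer that knowledge of the arm creates a false device effect in the primary analysis. Baseline is taken before allocation, so the arm can influence Follow-up only, and a bias confined to one arm mainly affects the secondary ANCOVA. Within a group, hiding the arm would not remove expectation, because the measurer still knows it is the Follow-up visit.

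**Conclusion.** The gap is real and no other section closes it: single readings, 8 of 10 at an extreme with no recorded level, and no withholding of Baseline values or arm, for the one primary endpoint that is not self-reported. The consequences are wider intervals from random re-location error and an opening for bias at Follow-up when the earlier value is known.

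The size cannot be derived from the documents. The 1.7-3.3% at Site 4 rests on an assumed taper, shift and thigh girth. The false-positive rates rest on assumed bias sizes, and the 30-leg column also on independent legs. Nothing here shows that a bias will occur or that it must favour the device. The point is worth acting on because the remedy is cheap.

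**What to change.** Amend section 6.7 in three ways:

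1. Take two readings per site at each visit, with the tape removed and repositioned between them, and analyse the mean.
2. At Baseline, find Site 4 as now and record its level as a distance above the top of the knee cap (Site 3). At Follow-up, tape at that distance.
3. Record Follow-up on a blank form that carries only the Site 4 distance. Withhold the Baseline girths until the form is complete.

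The cost is a few form fields, 20 readings in place of 10, and a few more minutes per visit. Subjects already measured at Baseline without a recorded level cannot be given one afterwards. Recording heights at the other sites, or using a measurer who did not open the envelope, can be left optional. The latter would mainly protect the between-group comparison.
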